RESEARCH PROTOCOL

The “*What is a Protocol?*” file on the HREB ethics website requested that applicants provide information about both the scientific and ethical aspects of their proposal. We will therefore divide this protocol description into those two sections.

1. Scientific Elements

(a) Background Research

In 2010 - 2011, more than 762,000 total knee arthroplasty (TKA) surgical procedures were performed across Canada (1). This number is expected to increase dramatically in the coming years with the growing older adult population and with the recently quantified TKA projections for younger patients (2). The growth of this procedure has resulted in increasing reports of dissatisfaction and poor outcomes such as increased pain, unmet expectations, reduced daily functioning (3), and compromised psychological health (4). Although suboptimal outcomes are not unusual in surgical procedures, there is a discrepancy in the proportion of poor outcomes associated with TKA compared to other arthroplasties. For example, 18-20% of patients following TKA report dissatisfaction (3, 5) compared to only 7% following a total hip arthroplasty (6). In response to these discrepant findings, there have been a significant number of studies that have identified psychological and psychosocial factors that are implicated in poor outcomes of TKA, even when controlling for medical factors such as surgical technique (7). This is not surprising given that more than 50% of adults undergoing TKA suffer from osteoarthritis, which has high comorbidity rates with mental disorders (8). Although psychological factors have been identified as contributing to poor outcomes, it is not clear whether an evidence-based psychological intervention can positively impact post-TKA sequelae. This study aims to pilot the effectiveness of an empirically supported intervention, mindfulness based stress reduction (MBSR), on post-TKA outcomes using a superiority randomized controlled trial (RCT) design.

TKA Outcomes. It is common for patients to have a successful TKA surgery but report dissatisfaction post-operatively (9), which has been largely attributed to post-operative pain (10) and restrictions in functioning and engaging in daily activities (3). Pain catastrophizing, defined as a tendency to magnify the threat of pain, is associated with the intensity of post-operative pain (11). Further, pre-surgical pain catastrophizing has also been linked to post-surgical pain and function (12). In some cases, the symptoms of pain following TKA surgery may become prolonged and debilitating, to the point where patients develop a chronic pain condition (13).

Predictors of Outcomes. It is essential to identify predictors of poor outcomes of TKA for targeted prevention initiatives. Female patients (14) and specifically those from low-income households (14) are at increased risk of reporting dissatisfaction following TKA. Dysfunctional coping style (15, 16) and lower internal locus of control (16) have been associated with poor TKA outcomes, and preoperative patient expectations are linked to dissatisfaction following TKA (5, 15). A growing body of research has demonstrated that psychological factors such as pain catastrophizing (17, 18), depression

(18), and anxiety (19) are significant predictors of persistent pain following TKA.

Interventions to Improve TKA Outcomes. Most of the targeted TKA pre-operative interventions to date have been education-focused (20, 21). A systematic review revealed that although pre-operative education can reduce anxiety, there is little evidence that it improves post-operative outcomes (26). Additional interventions, such as pre-operative exercises (22) or resistance training (23) exist, but the literature is mixed on whether they improve outcomes of TKA such as pain or physical functioning (24, 25). Although a large and growing number of studies have identified psychological and psychosocial factors as indicators of poor outcomes, research has not yet examined interventions targeting these risk factors directly.

Mindfulness Based Stress Reduction. In 2008, Drs. Ludwig and Kabat-Zinn published an editorial in JAMA describing the benefits of mindfulness (i.e., purposeful attention to the present with non-judgmental acceptance) in medicine and the growing body of evidence to support positive physical, mental, and psychosocial outcomes following mindfulness interventions. MBSR is the most widely used empirically-supported intervention that employs mindfulness techniques to address health holistically (27). A MBSR program typically consists of 8 weekly 2.5 hour sessions, home practice (typically 45 minutes per day, 6 days per week), and one day retreat. During the program, participants engage in a number of mindfulness practices (e.g., body scan, mindful movement, meditation) and discussions of their experiences, with the aim enhancing awareness to moment-to-moment experiences in a non-judging and accepting manner.

Health Outcomes. The growing body of literature is demonstrating the positive effects of MBSR on a variety of health outcomes (28). For example, a comprehensive systematic review that examined 115 randomized controlled trials found that, compared to wait list controls, MBSR significantly improved depression, anxiety, stress, quality of life, and physical functioning (28). With respect to pain-related outcomes, MBSR has been found to significantly reduce pain intensity and improve health-related quality of life among patients with chronic pain conditions, with the largest effect sizes demonstrated among those with arthritis (29), who comprise the largest proportion of TKA surgeries. Similar improvements in physical symptoms such as pain intensity, fatigue, and quality of life were demonstrated following MBSR among patients with chronic headaches (30). MBSR is also associated with reductions in pain catastrophizing, which is highly implicated in TKA, in chronic back pain patients compared to usual care or a cognitive-behavioural therapy group (31). Going beyond chronic pain conditions, MBSR has commonly been used as a weight-management strategy (32). According to a recent review, mindfulness interventions result in improvements in binge eating and dietary intake (34). This is of interest as obesity has been identified as a complicating factor in TKA influencing post-operative health outcomes (35), length of stay, and higher medical costs (36).

Preliminary Surgical-Related Outcomes. Despite this compelling evidence, there is little research examining MBSR in surgical contexts. One preliminary study investigating MBSR postoperatively following a spontaneous subarachnoid hemorrhage surgery found it resulted in significant decreases in ratings of depression and physical

stress, suggesting it was successful in both reducing psychological symptoms and improving homeostasis control mechanisms of the autonomic nervous system (37).

(b) General Overview of the Research Plan

The current research will consist of a pre-surgical MBSR course compared to a treatment-as-usual condition to evaluate post-surgical outcomes, including post-operative pain (severity and catastrophizing), improved physical functioning (interference and illness impact), post-surgery complications, and psychological factors including enhanced quality of life, reduced emotional distress (anxiety and depressive), enhanced cognitive skills, and improved sleep. The data will reveal if MBSR is feasible in a TKA population and determine if there are post-surgical benefits, as compared to the treatment as usual (TAU) group.

(c) Objectives, Research Design, and Hypotheses

Objective: The primary objectives are (a) to determine if an 8-week pre-operative MBSR program is feasible in a TKA population, and (b) to determine if this program results in reductions in post-operative pain (pain behavior, pain catastrophizing), improved physical functioning (pain interference, psychosocial illness impact), enhanced quality of life (global health), reduced emotional distress (anxiety and depression), enhanced cognitive skills (Cognitive Concerns), and improved sleep (fatigue, sleep disturbance) compared to TAU.

Research Design: Forty-five participants on the waitlist for a TKA will be recruited from Concordia Hospital Hip and Knee Institute – a facility that performs 800 TKA's per year. Participants will be divided into two groups: the MBSR group prior to surgery (30 participants, divided into two MBSR groups), and the TAU (15 participants; MBSR after surgery). The individuals in the MBSR group will receive a pre-operative 8-week community-based MBSR course, which includes group classes lasting 2.5 hours a week, 45-minutes of home practice 6 days per week, a 1-hour orientation session at the beginning, and a full-day silent retreat at the end. During the orientation, participants will complete the study measures for this study. Two weeks prior to the surgery at the pre-anesthesia clinic, patients will receive another short self-reported questionnaire between the MBSR intervention and TAU groups. Patients will subsequently receive post-operative questionnaires at the following regularly scheduled post-operative appointments: 6-8 weeks after surgery, and at 6 month and 1 year follow-ups. Clinic personnel, who are blinded to assignment, will administer these measures with all other regularly distributed clinical measures. Clinic personnel will also review the chart to inform researchers as to what physical condition contributed to the need for a TKA. The TAU group will have the opportunity to enroll in an MBSR course following the completion of the study (after approximately 1 year), at no cost.

Hypotheses: We predict that pre-operative MBSR will improve post-surgical outcomes including reductions in post-operative pain (pain behavior, pain catastrophizing),

improved physical functioning (pain interference, psychosocial illness impact), enhanced quality of life (global health), reduced emotional distress (anxiety and depression), enhanced cognitive skills (Cognitive Concerns), and improved sleep (fatigue, sleep disturbance) compared to TAU group.

MBSR is an empirically-supported intervention that has been used to examine various health outcomes and psychological factors in both health conditions (e.g., chronic pain; 29, anxiety and depression; 28, and binge and emotional eating; 32) and more recently, surgical populations (spontaneous subarachnoid hemorrhage surgery; 37). We are therefore confident that MBSR will improve the psychological factors and the physical health factors we described above.

(d) The Selection of Participants / Sample Size Calculations

TKA patients will be recruited from the TKA waitlist at Concordia Hospital Hip and Knee Institute— a facility that performs 800 TKA's per year. A Concordia Hospital Hip and Knee Institute staff member or a psychology graduate student on the project will contact all participants, ensuring the inclusion/exclusion criteria are met. Participants will be ensured that their participation is completely voluntary, and will be reminded that assignment to treatment conditions is completely random; therefore, participants will not feel obligated to participate, but will know receiving MBSR before their surgery is not guaranteed.

The sample size was estimated based on G*Power statistical software using a 2:1 approach with a large effect size (Cohen's $d = 0.8$). We will recruit 30 patients for the intervention where they will be divided in 2 groups that will consecutively run. The third TAU group will include 15 patients. This will yield 45 total participants. A 2:1 approach is used to assess within person change pre- and post-surgically given the pilot nature of the study and to protect against up to 20% attrition in the intervention group.

(e) Behavioural and Diagnostic Data

A variety of data will be collected during the initial telephone screening to ensure that participants meet our inclusion criteria. A phone screen template will be used to standardize the recruitment process. Because phone screening is conversational, the study description on the phone screen form has phrases that are italicized, and these are the key points that the phone screen interviewer will convey. We will be collecting information about age, sex, and language that they can read and understand. We will ask whether they are currently on the waitlist for a TKA, and whether the surgery they are waiting for is their first surgery (i.e., not a revision surgery). We will also be asking whether participants have ever been enrolled in an MBSR program or any other mindfulness course before, and if so, when it took place. All of these questions are very important in deciding whether participants are eligible for participating in this study.

After participants are screened for eligibility and provide verbal consent, they will be mailed out packages explaining MBSR in more detail, include two copies of consent forms, and a return envelope. After randomization, those in the MBSR group will complete study measures prior to their pre-operative MBSR course (at an orientation

session). These measures include: Patient- Reported Outcomes Measurements Information System (PROMIS) scales (Cognitive function, Fatigue, Pain Interference, Pain Behavior, Sleep Disturbance, Psychosocial Illness Impact, Global Health, Anxiety, and Depression scales (see: www.healthmeasures.net for information pertaining to NIH PROMIS initiative), a demographics form, the 13- item Pain Catastrophizing Scale (38), and the Five Facet Mindfulness Questionnaire (41). Two weeks prior to the surgery at the pre-anesthesia clinic, patients will receive another short self-reported questionnaire, as well as a questionnaire asking about participation in any other prehabilitation courses offered through the Hip and Knee Institute or any other centre. In PAC, clinic personnel will review the chart to inform researchers as to what physical condition contributed to the need for a TKA. Patients will subsequently receive post-operative questionnaires at the following regularly scheduled post-operative appointments: week 6-8, 6 month, and 1 year. Clinic personnel, who are blinded to assignment, will administer these measures with all other regularly distributed clinical measures, and they can complete while waiting for their appointment.

(f) Data Analysis

We will be looking at changes in outcomes from before to after the MBSR intervention in (a) the MBSR compared to TAU participants, and (b) within the MBSR participants. We will focus on within-persons mean differences using paired samples t-tests within the intervention group. To determine the impact of MBSR on the postoperative TKA outcomes, we will conduct multivariate analyses of variance of conceptually linked dependent variables (i.e. pain variables, mental health variables) with significant results followed up by Tukey post-hoc tests.

(g) Timeline

We hope to begin recruitment after we have obtained ethics approval from both the University of Manitoba and Concordia Hospital Hip and Knee Institute in August 2017. We hope to run the MBSR courses in Fall 2017, run by a teacher ([name]) with extensive MBSR and yoga training. We anticipate the total duration of this study will August 2017 to August 2019. We will renew our ethics protocol annually, as per HREB requirements.

(h) Definition of Adverse Events

The adverse events should be limited to a reaction to the MBSR course. Participants will be fully informed about MBSR, and what participation in the course will include. In the unlikely event that a participant feels extreme discomfort in a meditation position (e.g., their knee hurts too much), the MBSR instructor has been trained to manage these situations. If additional support is warranted, appropriate resources will be implemented as described in the ethics form.

(i) Budget

Professional Assistance:

MBSR instruction:

\$18,500 in fee payment to qualified MBSR instructor.

$[(45 \text{ participants} \times \$400/\text{participant}) + \$500 \text{ orientation fee} = \$18,500]$

A certified, trained MBSR instructor is required to deliver the MBSR course. The course will be offered to the TKA patients at no cost to themselves, so as to maximize enrollment. No honorariums will be provided to the participants, as the waiver of the MBSR fee is already significant. The MBSR instructor's time, her securing of accommodations in which to hold the sessions, and providing all necessary resources (i.e., workbooks) are included in the fee of \$400/participant. The instructor's time for conducting the 1 hour orientation meetings for all 3 groups is \$500.

See letter from MBSR instructor for quote (appended to this application).

TKA clinic assistance:

$[(\$60/\text{hr} \times 143 \text{ hrs}) + \$150] = \$8,730$

\$8,730 is required for the assistance of the TKA clinic staff. As TKA patients will be recruited from the clinic, access to standard clinic measures will be required, and administration of the additional study-specific measures will be performed by clinic staff at the patient's scheduled appointments, compensation to clinic staff is required. Clinic staff have identified the following time commitments:

1. Pulling waitlist patient info (contact #'s & expected date of sx): 4 hrs
2. Query to pull pre-op Oxford (and other) data for 30 pts: 4 hrs
3. Administer, fill & send post-op questionnaire packages at 6 wks, 6 mo, 12 mo: $\frac{1}{2}$ hr per visit = 45 hrs
4. Query to pull all post-op Oxford, Satisfaction data for 30 pts: 30 hrs
5. Calling and recruiting of patients (mail-out consent & pre-op packages) $\frac{1}{2}$ hr per patient (say 25% rate of enrollment) + mailing costs (~\$5 per, incl. return shipping) = 60 hrs + \$150 mailing

The typical research staff rate is \$60/hr, covering wages and a portion of overhead, for a total of \$8,580, plus \$150 for mailing.

All materials and supplies are currently available and do not require additional budgeting.

Anesthesia residents and graduate student involvement are covered by respective departmental obligations and do not require additional budgeting.

NOTE: This budget exceeds the limit of \$25,000 available from the UCRP; however, Drs. [name] and [name] will cover the \$2,230 of above-budget costs from their start-up funding.

2. Ethical Elements

(a) Potential Benefits to Participants and Others

Ours will be the first study to test pre-surgical MBSR on post-surgical TKA outcomes. TKA patients are a group of patients growing exponentially and are known to have poor health outcomes. MBSR is a relatively risk-free, empirically supported intervention that has potential to alleviate or lessen these outcomes. Therefore, it should be of interest to TKA patients, especially considering the benefits can be applied to all aspects of their lives, not just in regard to their upcoming surgery. This study may also provide insight on the feasibility of such an intervention to this surgical population. It may allow further research into an adapted version of the MBSR, which could enhance accessibility and service delivery. It may also have broader health and economic implications.

(b) Potential Harms to Participants and Others

There is a possibility that some participants might find a particular meditation posture (e.g., sitting) uncomfortable; however, appropriate modifications will be suggested by the MBSR instructor. Patients may experience temporary discomfort from answering questions related to emotional health; however, resources will be provided if warranted. In exceptional circumstances staff Psychologist, [name] (co-PI), will be contacted by research personnel.

(c) Alternative Treatments or Procedures

The participants randomly assigned to the MBSR group will receive MBSR prior to surgery and the participants who are assigned to treatment as usual will receive MBSR 1 year after surgery.

(d) Minimization of Potential Harms

Concerns regarding MBSR will be minimized through the prescreening and through the forms that thoroughly explain MBSR. All participants who consent will receive these documents and be reminded that if they have any concerns about participation, to not hesitate to ask.

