Statistical Analysis Plan

We will be looking at changes in outcomes from before to after the MBSR intervention in (a) the MBSR compared to TAU participants, and (b) within the MBSR participants. We will focus on within-persons mean differences using paired samples t-tests within the intervention group. To determine the impact of MBSR on the postoperative TKA outcomes, we will conduct multivariate analyses of variance of conceptually linked dependent variables (i.e. pain variables, mental health variables) with significant results followed up by Tukey post-hoc tests.

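### The MBSR arm is taught in two shared classes, but the pooled paired t-tests (and the MANOVA, if run by arm) make no allowance for correlation within a class

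*Protocol*

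**What the plan says.** Protocol 1(c) describes the MBSR arm as "30 participants, divided into two MBSR groups", with "group classes lasting 2.5 hours a week" for eight weeks and a shared full-day retreat. Section 1(d) repeats the division and adds that the two courses follow one another: "they will be divided in 2 groups that will consecutively run". TAU patients are offered MBSR only about a year after surgery (1(c) and 2(c)), so nothing groups them by class while outcomes are collected.

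On analysis, the SAP (and the identical text in Protocol 1(f)) states: "We will focus on within-persons mean differences using paired samples t-tests within the intervention group". The effect of MBSR on post-operative outcomes is then tested by MANOVA on related outcomes, with Tukey follow-up. Class appears in neither step.

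The sample size in 1(d) was obtained from G*Power "using a 2:1 approach with a large effect size" of d = 0.8, giving 30 + 15 = 45. Alpha, sidedness, power and any allowance for class are not stated. The 2:1 ratio is justified by the interest in within-person change and by possible attrition of up to 20% in the intervention arm.

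**The concern.** Patients who spend eight weeks in the same class share its group dynamics and its place in the calendar. Their outcomes may therefore be more alike than those of patients in different classes. TAU patients have no such link. This is a partially nested design: one arm clustered, the other not.

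A paired t-test on 30 change scores divides their variance by 30 as if each were a separate piece of information. With a positive class ICC, the mean change varies more than that, and one class that happens to do well can produce a significant within-arm result. The between-arm comparison suffers less, because the unclustered TAU mean contributes two thirds of the variance under independence (1/15 out of 1/30 + 1/15). The test that the plan says it will focus on is the one most exposed.

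**Working it through.** **Inputs.** From the documents: 30 MBSR patients in two classes, 15 TAU patients, d = 0.8, attrition up to 20% in the MBSR arm. Inferred: m = 30/2 = 15 per class, or 24/2 = 12 after 20% attrition. Assumed: class ICC of 0.01 to 0.10, and two-sided 5% tests for the error rates.

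**The plan's own figure.** With one-sided alpha 0.05, 80% power and independence (all assumed), the normal approximation gives a TAU arm of (1.645 + 0.842)² × (1 + 1/2) / 0.8² = 14.5, so 15, with 30 in MBSR and 45 in total. The noncentral t calculation also gives 15/30, with power 80.1%. The figure reproduces with nothing left over for a design effect. Under a two-sided 5% test the t-based requirement is 60, and 45 patients have about 70% power.

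**Formulas.**
- Design effect in the MBSR arm: DE = 1 + (m − 1) × ICC.
- Paired test: true SE / naive SE = √DE; effective n = 2m/DE.
- Between arms at m = 15: variance ratio = (DE/30 + 1/15) / (1/30 + 1/15) = (DE + 2)/3; the SE ratio is its square root.
- Type I error: simulation of the uncorrected two-sided 5% t-tests with two classes and a normal class effect. The two-sample t-test stands in for one outcome of the MANOVA.

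**Results with 15 per class.**

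| ICC | DE | Paired SE ratio | Effective n | Paired type I error | Between-arm SE ratio | Between-arm type I error |
|---|---|---|---|---|---|---|
| 0.01 | 1.14 | 1.07 | 26.3 | 6.6% | 1.02 | 5.5% |
| 0.02 | 1.28 | 1.13 | 23.4 | 8.3% | 1.05 | 6.1% |
| 0.05 | 1.70 | 1.30 | 17.6 | 13.2% | 1.11 | 7.9% |
| 0.10 | 2.40 | 1.55 | 12.5 | 20.8% | 1.21 | 10.9% |

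Worked line for ICC 0.05: DE = 1 + 14 × 0.05 = 1.70; √1.70 = 1.30; 30/1.70 = 17.6; (1.70 + 2)/3 = 1.233 and √1.233 = 1.11.

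**Results with 12 per class.** DE = 1 + 11 × ICC = 1.11 / 1.22 / 1.55 / 2.10 at the same four ICCs. Paired type I error is about 6.3% / 7.5% / 11.5% / 17.7%.

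Repeat simulations of 100,000 or more runs agree with these error rates to within about 0.2 percentage points.

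**The case against.** **The bias is conditional.** A reader might infer that the intervals are certainly too narrow. The documents do not support that: they give no ICC, and at 0.01 the between-arm error is only 5.5%. This objection stands, and every figure above depends on the assumed range.

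**The MANOVA may already separate the classes.** Protocol 1(d) says "The third TAU group will include 15 patients", the budget in 1(i) counts three groups for orientation, and Tukey tests are needed only with three or more groups. A three-level MANOVA (class 1, class 2, TAU) is therefore possible. Section 1(c) describes two groups, and neither document settles it. The between-arm figures hold only if the MANOVA is run by arm. The pooled paired t-tests ignore class on either reading.

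**The paired tests have a larger weakness.** Section 1(d) ties within-person change to before and after surgery, so such a change also reflects surgery and time, and no design effect repairs that. The efficacy objective in 1(c) is the comparison with TAU, where the inflation is smaller. Both points are fair. They limit what the within-arm tests can show, but the plan still makes those tests its focus.

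**Overstated power.** A reader might infer that the trial's power claim is too high. No power is stated, so there is no figure to correct. In simulation, the planned uncorrected two-sided test at d = 0.8 goes only from about 0.70 at ICC 0 to about 0.67 at ICC 0.10. Larger falls belong to a test with a corrected SE. What can be said is that the sample size carries no allowance for class.

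**The shared instructor.** Section 1(g) has one teacher running the courses, and a reader might count this as a source of clustering. A factor common to both classes adds no variance between them. It limits generalisability instead.

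**Two classes cannot estimate an ICC.** True: a random class effect would leave 1 degree of freedom, with a two-sided 5% critical value of 12.7. Fixed assumed ICCs avoid the need for an estimate.

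**Conclusion.** The point holds in conditional form. The MBSR arm is clustered in two classes, TAU is not, and the analysis on which the plan focuses makes no allowance for it. If the class ICC lies between 0.01 and 0.10, a nominal 5% paired test has a true error of about 6.6% to 21% with 15 per class, or 6.3% to 18% with 12. The between-arm test, if run by arm, has about 5.5% to 11%. These figures rest on the assumed ICC range, equal classes and a univariate stand-in for the MANOVA. The by-arm estimates need not change; the gap is in the stated uncertainty. Because this is a pilot, the proportionate response is a reporting addition, not a redesign.

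**What to change.** Add to the SAP:

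1. State that MBSR patients are nested in two classes and TAU patients are not, and say whether the MANOVA has two levels (arm) or three (each class and TAU).
2. Keep the by-arm estimates. Prespecify a partially nested sensitivity analysis for each outcome: multiply the variance of the MBSR-arm mean (or mean change) by 1 + (m − 1) × ICC, with m the analysed class size, at fixed ICC 0.01, 0.05 and 0.10, and no inflation in TAU. Using the analysed m matters: fixing the multiplier at 1 + 14 × ICC would over-correct after attrition.
3. Report these intervals beside the unadjusted ones, and show MBSR results separately by class.

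Add to Protocol 1(d) that the sample size assumes ICC = 0.

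No ICC threshold for calling a finding supported is proposed. The documents give no basis for choosing one, and readers can judge from the range.

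The cost is a few lines of text, one extra table and wider intervals. Recruitment, randomisation and course delivery are unaffected.

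### The plan defines only reactions to MBSR as adverse events but never asks about or records them, so an absence of reports could not be interpreted

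*Protocol*

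**What the plan says.** Protocol section 1(h) sets the scope: "The adverse events should be limited to a reaction to the MBSR course". Its example is a participant in marked discomfort in a meditation posture: "e.g., their knee hurts too much), the MBSR instructor has been trained to manage these situations". For anything further it says "If additional support is warranted, appropriate resources will be implemented as described in the ethics form"; that form is not among the documents.

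Two other provisions touch on harm. Under section 2(b), the staff psychologist "will be contacted by research personnel" in unusual cases. Under section 2(d), those who consent will "be reminded that if they have any concerns about participation, to not hesitate to ask".

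Section 1(c) describes the course as "group classes lasting 2.5 hours a week, 45-minutes of home practice 6 days per week", for 8 weeks, with a 1-hour orientation and a full-day retreat. Section 1(d) plans 30 MBSR and 15 TAU patients and allows for up to 20% attrition in the MBSR arm.

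Section 1(e) lists the measures: PROMIS scales, demographics, the Pain Catastrophizing Scale and a mindfulness questionnaire. At the pre-anesthesia clinic there is a short self-report form, whose content is not itemised, and a question about other prehabilitation courses. Postoperative questionnaires follow at 6 to 8 weeks, 6 months and 1 year. No adverse event item is listed. Section 1(f) and the SAP plan paired t-tests and multivariate analyses of variance, with no summary of harms.

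**The concern.** A definition of adverse events is useful only if someone is charged with finding and recording them. Section 1(h) names no question, form, recorder, time window or grading. The instructor is given a task of managing discomfort, not of telling the study team about it, so even a reaction seen in class has no stated path into the data.

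This bears on the first primary objective, whether the course is feasible in patients awaiting knee replacement. The protocol does not say what feasibility comprises, but whether patients with a painful knee can tolerate the course is a natural part of it. Section 2(a) also describes MBSR as carrying little risk, while sections 1(h) and 2(b) both foresee discomfort from posture. If nobody is asked, the trial can neither support nor question that description. A patient who leaves because practice hurts will also look the same as one who leaves because of scheduling. Data not collected at the time cannot be recovered at analysis.

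**Working it through.** The documents state no adverse event rate, count or limit, so there is no harm figure to reproduce. The check has four parts.

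**1. Points of contact, side by side.**

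| Setting | What the documents provide | Reaction asked about or recorded? |
|---|---|---|
| Class and retreat | Instructor manages discomfort (1(h)) | Not stated |
| Home practice | None specific | Not stated |
| After leaving the course | None specific | Not stated |
| Pre-anesthesia clinic | Short form, course-participation question (1(e)) | No item listed |
| 6 to 8 weeks, 6 months, 1 year | Questionnaires (1(c), 1(e)) | No item listed |
| Any time | Participant may raise concerns (2(d)); psychologist in unusual cases (2(b)) | Passive; no record described |
| Analysis | t-tests and MANOVA (1(f), SAP) | No harm summary |

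**2. Where the exposure lies (1(c)).**
- Home: 45 min × 6 days × 8 weeks = 2,160 min = 36 h.
- Weekly classes: 2.5 h × 8 = 20 h, plus the retreat, whose length is not given.
- With the retreat assumed to last 6 to 8 h, supervised time is 26 to 28 h, and home practice is 36/62 to 36/64, or 58% to 56% of the total (orientation hour left out).

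This is a share of practice time. It is not a share of events missed.

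**3. Dropouts (1(d)).** 20% × 30 = 6 patients.

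**4. What an absence of reports would mean.** Let p be the true risk of a reaction per patient and q the share of reactions that reach the study. Both are assumptions, since the documents give neither. Among 30 patients the expected number of reports is 30pq, and the chance of none is (1 − pq)^30.

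| p | q = 1 | q = 0.5 | q = 0.25 | q = 0 |
|---|---|---|---|---|
| 5% | 1.5; 21% | 0.75; 47% | 0.375; 69% | 0; 100% |
| 10% | 3.0; 4% | 1.5; 21% | 0.75; 47% | 0; 100% |
| 20% | 6.0; 0.1% | 3.0; 4% | 1.5; 21% | 0; 100% |

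Each cell gives expected reports and the chance of none. With q unknown, silence is compatible with every row. If all patients are asked (and taking q = 1), zero reports gives a one-sided 95% upper limit of 1 − 0.05^(1/n): 9.5% for n = 30 and 11.7% for n = 24, if the 6 who leave are not reached. For the 15 TAU patients it is 1 − 0.05^(1/15) = 18.1%, so a background rate from that arm would be descriptive only.

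**The case against.** The plan is not silent outside the classroom. Participants are told to raise concerns, research personnel can bring in the psychologist, and the ethics form may hold more. Section 1(a) says MBSR sessions include discussion of participants' experiences, so a problem met at home may come up at the next class. Pain, anxiety and depression scales are collected and could show worsening at group level.

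All of this is fair, and some of it stands. These routes could bring individual reactions to someone's attention. None of them asks every participant, and none is tied to a record. Section 1(h) cites the ethics form for support resources, not for recording. The scales are to be analysed as means, so they neither identify a reaction nor explain a departure.

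The same facts rule out several stronger readings that a reader might infer:

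- *Reactions reach the study only if the instructor sees them in class.* The text does not say this. It gives the instructor no reporting role at all, and it does offer passive routes elsewhere.
- *The harm count is biased toward zero.* No count is planned, so there is no estimate to be biased.
- *Home practice's share of the hours measures the events missed.* It does not, because a reaction at home can be mentioned later.
- *The TAU patients' later course is a hole in the harm data.* Section 2(c) says those "assigned to treatment as usual will receive MBSR 1 year after surgery", and section 1(c) places that offer after study completion. Leaving it out biases neither the MBSR-arm result nor the randomised comparison.

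**Conclusion.** The concern holds as an omission in collection and reporting. Course reactions are the only adverse events defined. Nothing listed in the protocol or SAP asks about them, records them or summarises them in class, in home practice or after dropout. Because the definition is tied to the course, the TAU arm cannot supply a background rate, which matters when waitlisted patients may have worsening knee pain without MBSR. An absence of reports would therefore be uninterpretable for tolerability.

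The size of any under-recording cannot be computed. What can be stated is 36 h of home practice against 20 h of weekly classes plus a retreat, up to 6 of 30 patients lost from the course, and the 9.5% upper limit that would become available if all 30 were asked and none reported a reaction.

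The conclusion assumes that the ethics form and the un-itemised pre-anesthesia form contain no harm question. If either does, the protocol should say so and the point narrows to the missing tabulation. The planned efficacy comparison is unaffected. The change should be made because it is cheap and cannot be made retrospectively.

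**What to change.** 1. Add one neutrally worded, patient-completed item to the pre-anesthesia questionnaire in both arms, covering new or worse knee pain, falls or emotional distress since enrolment, whatever the cause. Any part that refers to the course should be returned sealed or sent directly to the research team, so that clinic personnel stay blinded.
2. Have the research team put the same item, and a question on the reason for leaving, to anyone who stops the course. Do not rely on those patients completing the clinic form.
3. Have the instructor log each event handled in class and pass the log to the study team. Name the recorder and the time window in section 1(h).
4. Add a harm summary to the SAP: number and percentage with a report, by arm, with exact confidence limits and the number actually asked. In the MBSR arm the denominator is all who started the course. With 30 and 15 patients this should be descriptive.

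The cost is one more question for patients, a brief contact with up to about 6 leavers, a short log and one table. The downsides are a small unblinding risk that has to be managed, reliance on recall back to enrolment, and a harm figure that may look less favourable than silence would.
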